So far, recent immune-modulatory therapies decrease MS relapse rate and disease severity¹⁶ but they do not slow the disease process. Because such therapies, unfortunately, do not affect accumulation of MS disabilities and comorbidities and because at least some MS related impairments are inactivity related rather than a result of non-reversible tissue injury, exercise rehabilitation therapy has become an important part of overall MS treatment. Indeed, a multitude of low to moderate intensity **exercise intervention studies in MS** already reported small (+10-15%) but significant improvements in muscle strength and exercise capacity³. Surprisingly however, **effects are lower compared to healthy controls and some other disease populations**. In an attempt to further improve rehabilitation outcome we therefore recently performed higher intensity training (HIT) studies in an animal MS model (Experimental Autoimmune Encephalomyelitis, EAE¹⁷) and in MS patients¹⁸. Although results are promising with substantially improved (+25-30%) muscle strength and exercise capacity following 8-12w of exercise^{17, 18} most MS subjects reported **higher post exercise muscle fatigue and overall perceived exertion rates (BORG: 14.7±1.5 vs. 12.7±1.3)** compared to low-to-moderate intensity training¹⁵.

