Figure 4. Muscle carnosine concentrations (mmol/kg WW) in EAE rats (animal MS model), without (EAE CON, n=13) and with carnosine (EAE CA, n=13) or β -alanine (EAE BA, n=13) supplementation. *p<0.05 compared to control group.

Research objectives

Increasing evidence favours exercise therapy as an efficient tool to counteract inactivity related secondary symptoms in MS. Furthermore, exercise therapy may affect MS-associated muscle contractile and energy supply dysfunctions. So far, low to moderate intensity exercise rehabilitation has shown to induce small but consistent improvements in several functional parameters. High intensity exercise training in MS seems to further improve this. However, although results are promising, impairments in both muscle contraction and energy supply probably attenuate therapy outcome. In keeping with the above described physiological role of skeletal muscle carnosine and because muscle carnosine content may be lower in MS, **the primary aim of the present project is to investigate whether carnosine loading improves exercise therapy outcome (exercise capacity, body composition) and performance in MS.** If the latter hypothesis can be confirmed, muscle carnosine loading could be a novel intervention to improve exercise capacity and muscle function in this population.

Ergogenic potential of muscle carnosine loading and exercise therapy in MS

So far, it is clear that β -alanine intake enhances exercise capacity of untrained, trained and aged individuals by improving contractile properties, maintaining higher intracellular energy levels and optimizing training adaptations. Because early fatigue of contracting musculature during rehabilitation is the predominant cause of exercise cessation, postponing exercise-induced fatigue by β -alanine supplementation will be clinically very relevant (improving exercise therapy efficiency). Consequently, we aim to research the ergogenic potential of β -alanine intake in MS rehabilitation and **hypothesize that β -alanine supplementation in combination with exercise therapy optimizes therapy outcome (exercise capacity, body composition) and performance in this population.**

METHODS

Subjects

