Twenty multiple sclerosis (MS) patients, diagnosed according to the McDonald criteria, and twenty healthy controls (HC), aged >18y will be included following written informed consent. Subjects will be excluded if they experience contraindications to participate in moderate to high intensity exercise, already participate in another study, experienced an acute MS exacerbation <6 months prior to the start of the study or have an EDSS score >3. This study will be performed in accordance with the Declaration of Helsinki and will be registered at ClinicalTrials.gov.

Study design

Following inclusion, baseline measurements (PRE) will be performed in MS patients (n=20) and HC (n=20). First, exercise capacity (maximal graded exercise test) will be evaluated. Prior to the maximal exercise test, heart function will be assessed by an experienced medical doctor, followed by measurement of whole body composition (DEXA). Furthermore, maximal strength of the back- and abdominal muscles will be assessed to evaluate core stability (important during prolonged cycle training). Hereafter, MS patients and HC will be randomly allocated to one of four intervention groups following 6 months of moderate-to-high-intensity cardiovascular exercise therapy with (MS β , n=10; HC β , n=10) or without (MS_{placebo}, n=10; HC_{placebo}, n=10) β -alanine supplementation. Groups not receiving β -alanine supplements, will receive placebo tablets that will be identical in taste and appearance. Following 6 months of exercise training (POST) measurements will be performed similar to baseline.

Exercise program

Moderate-to-high-intensity cardiovascular exercise therapy

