The supplementation protocol of β -alanine (Etixx $^{\circledR}$ Omega Pharma Belgium NV) involves oral intake of 4 x 800mg (3.2g/day^{29, 43}) daily with at least 2h apart of slow-release β -alanine during the first 12 weeks. After this loading period, subjects will receive a maintenance dose of 2 x 800mg (1.6g/day) β -alanine for the remaining study duration. Placebo groups will follow the same supplementation protocol with placebo tablets that will have identical taste and appearance. All subjects will be advised to take the tablets together with meals. This supplement is frequently used to improve sport performances in athletes. The beta-alanine supplement consists of beta-alanine, hydroxymethylcellulose, cellulose, silicon dioxide, magnesium stearate and zinc. In some cases, taking beta-alanine can provoke a tingling feel (paresthesia) on the skin which is reversible within the hour. However, this is not dangerous and completely reversible. To prevent this paresthesia, β -alanine tablets will consist of slow-release β -alanine which, together with the spread intake throughout the day, will not provoke this discomfort.

Measurements

Exercise capacity & serum lactate. Exercise capacity will be assessed using a maximal (12-lead ECG) graded cardiopulmonary exercise test (♂: 30W+15W/min, ♀: 20W+10W/min) with pulmonary gas exchange analysis (Jaeger Oxycon®). Subjects will perform the exercise test on their personal bicycle (Cyclos2® Leipzig, Germany). VO₂, VE, RER will be monitored and 2min capillary blood samples will be obtained to analyse blood lactate concentrations (Analox®) and determine the anaerobic threshold before, during and after exercise. RER values will be evaluated to verify if the test was performed maximally (RER >1.1).

Body composition Whole body fat and lean tissue mass will be obtained using Dual Energy X-ray Absorptiometry scan (DEXA) (Hologic Series Delphi-A Fan Beam X-ray Bone Densitometer, Vilvoorde, Belgium). A calibrated analogue weight scale (Seca®) will be used to measure total body mass.

Statistical analysis

Baseline differences between groups and post-intervention differences will be analysed using an unpaired student's t-test and a 4x2 ANOVA for repeated measures, respectively (SAS Institute®). The threshold for statistical significance will be set at p<0.05.

Reference List

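### MS versus healthy-control differences in level are analysed with no sex or age term and no stated matching, so they may reflect sex or age mix; the randomised comparison within MS is not biased (minor)

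*Combined protocol and SAP*

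**What the plan says.** All references are to the combined protocol and SAP.

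- **Statistical analysis.** "Baseline differences between groups and post-intervention differences will be analysed using an unpaired" Student's t-test and a "4x2 ANOVA for repeated measures, respectively", at p<0.05. No covariate is named, and the groups in the t-test are not identified.
- **Subjects.** Twenty MS patients and "twenty healthy controls (HC), aged >18y will be included following written informed consent". There is no upper age limit, no sex criterion and no matching.
- **Study design.** "baseline measurements (PRE) will be performed in MS patients (n=20) and HC (n=20"), and only then is each population randomised to β-alanine or placebo, 10 per arm. No stratification factor is stated.
- **Research objectives.** The primary aim is to "investigate whether carnosine loading improves exercise therapy outcome (exercise capacity, body composition) and performance in MS". No objective on MS-versus-HC level is stated.
- **Measurements.** The exercise test uses a steeper ramp for men (30 W + 15 W/min) than for women ("20W+10W/min) with pulmonary gas exchange analysis"), so sex is recorded and is treated as relevant to the test.

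**The concern.** Supplement or placebo is randomised; having MS or not is not. Exercise capacity and body composition are the outcomes, and the protocol itself treats sex as relevant to the exercise test. If the two populations differ in sex or age mix, their mean levels can differ with no effect of MS. The planned tests cannot separate the two explanations. Three comparisons are exposed: the baseline t-test if it compares MS with HC, the group main effect of the ANOVA, and any contrast of an MS arm with an HC arm.

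The risk is that a significant difference in level is reported as a consequence of MS when it comes from recruitment. If the sex mix is equal, the opposite problem arises: unexplained sex variance inflates the error term and the unadjusted test loses power.

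**Working it through.** **Inputs from the documents.** 20 MS and 20 HC; four arms of 10; significance level 0.05 (two-sided assumed, as sidedness is not stated). The plan gives no SD, effect size, power or sex mix, so it has no figure of its own to reproduce.

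**Assumed inputs.** Male:female ratio of mean capacity r = 1.3 or 1.5; within-sex CV 15, 20 or 25%; SD = CV × the sex-specific mean; no disease effect. The plan does not say whether capacity is absolute or per unit of body mass.

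**1. Spurious difference.** With the female mean set to 1, a group with k men of 20 has mean 1 + (r − 1)k/20. At r = 1.3, 6 men gives 1.09 and 12 men gives 1.18, a difference of 0.09 with no effect of MS.

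**2. Hand check at r = 1.3, CV 20%.**

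- Within-sex variances: women 0.20² = 0.0400, men 0.26² = 0.0676.
- Within-sex part of each group's variance: 0.3 × 0.0676 + 0.7 × 0.0400 = 0.0483 (6 men); 0.6 × 0.0676 + 0.4 × 0.0400 = 0.0566 (12 men).
- Between-sex part, which the t-test counts as noise: 20 × 0.3 × 0.7 × 0.3²/19 = 0.0199; 20 × 0.6 × 0.4 × 0.3²/19 = 0.0227.
- SE used by the t-test, 6 vs 12: √[(0.0483 + 0.0199 + 0.0566 + 0.0227)/20] = 0.0859. Actual SE at that fixed mix: √[(0.0483 + 0.0566)/20] = 0.0724.
- Rejection needs a difference beyond 2.024 × 0.0859 = 0.174. Upper tail: z = (0.174 − 0.090)/0.0724 = 1.16, probability about 0.12. The lower tail is negligible. Simulation gives 0.135.
- At 6 vs 6 the difference is 0, the t-test SE is 0.0826 and the actual SE is 0.0695. The rejection probability is P(|z| > 2.024 × 0.0826/0.0695 = 2.41), about 0.016. Simulation gives 0.021.

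**3. Simulated false-positive rate of the baseline t-test** (100,000 runs per cell; CV 15/20/25%)

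| Men, MS vs HC | r = 1.3 | r = 1.5 | With sex in the model |
|---|---|---|---|
| 6 vs 6 | 1.1 / 2.1 / 2.8% | 0.1 / 0.6 / 1.3% | about 5% |
| 6 vs 8 | 2.3 / 3.1 / 3.7% | 0.8 / 1.7 / 2.5% | about 5% |
| 6 vs 10 | 6.8 / 6.7 / 6.3% | 5.6 / 6.7 / 6.8% | about 5% |
| 6 vs 12 | 17.2 / 13.5 / 11.1% | 22.9 / 19.2 / 15.8% | about 5% |
| 6 vs 14 | 34.5 / 24.6 / 18.4% | 54.3 / 40.3 / 31.1% | about 5% |

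**4. How likely such gaps are.** If both groups come from a common 50:50 source, a gap of 4 or more men has probability 0.268 and a gap of 8 or more 0.017. Averaged over such chance gaps, the rate is 5%. It rises only if the sources differ: 6-8% for 30% vs 40% men and 9-18% for 30% vs 50%.

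**5. Power at equal mix (6 vs 6), for an assumed 15% MS deficit.** Unadjusted 29-76%; with sex in the model 50-91%.

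**6. Age.** Assume 0.5-1% of capacity per year and a gap of 5-10 years, in either direction: a shift a of 2.5-10%. At 6 vs 10 men (30% vs 50%) the HC excess from sex alone is 1.15/1.09 − 1 = 5.5% (r = 1.3) or 1.25/1.15 − 1 = 8.7% (r = 1.5). Net bias is (1 + sex bias)(1 ± a) − 1, which runs from 1.055 × 0.90 − 1 = −5.0% to 1.087 × 1.10 − 1 = +19.6%. The sign cannot be known in advance.

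**7. The ANOVA.** The false-positive rate for the group main effect is 5.5-5.9% at 6 vs 10 men and 11-28% at 6 vs 14. Group-by-time stays at 5% if gains do not depend on sex or level. If gains are proportional to level it is 5-6% at 6 vs 10. At 6 vs 14 it is 6-8% for a 12.5% gain and 7-14% for a 27.5% gain. Those gains are midpoints of the ranges in the Introduction: "small (+10-15%) but significant improvements in muscle strength" and "substantially improved (+25-30%) muscle strength and exercise capacity".

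**8. The randomised MS contrast (10 vs 10).** In simulation with no sex term, mean bias is 0.00 SD and the false-positive rate is 4.7-5.3%. An assumed sex effect of 1 SD raises the SE on POST level from 0.45 to 0.50 SD. The SE on change stays at 0.28 unless sex alters the change. The chance that the MS arms differ by 4 or more women is 14% with 14 women among the 20, and 17-18% with 8 to 12.

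**The case against.** The strongest objection is relevance. The aim concerns supplementation in MS, and no conclusion about MS-versus-HC level is planned. The harm is a possible misreading rather than a stated inference. This stands, and it sets the weight at minor.

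The target of the t-test is also open. The Methods mostly use the word groups for the arms, so the baseline test may be a balance check of β-alanine against placebo within each population. Those contrasts are randomised, and the baseline part of the concern would then fall away. On the other side, a t-test compares two groups, and the PRE measurements are taken in two populations before allocation. The text does not settle it. The ANOVA main effect and arm contrasts across populations remain exposed on either reading.

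The size is assumed throughout, and small imbalances do no harm to the error rate: up to 6 vs 8 men the test stays below 5%. This stands too. Material inflation needs a large gap or sources that differ in sex mix, and the documents indicate neither.

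A reader might infer that the primary result is confounded. The documents do not support that, because β-alanine or placebo is allocated at random within MS. Nor can the 1.5 ratio of the test ramps be read as an observed sex difference in capacity; it is a test setting.

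**Conclusion.** The point holds as a minor, secondary one. The plan has no sex or age term and states no matching, so MS-versus-HC differences in level are observational and may reflect sex or age mix. Under the assumed ratios and CVs, the effect on the baseline test ranges from conservative behaviour with loss of power (equal or nearly equal mix) to a false-positive rate of 11-23% at 6 vs 12 men. Higher rates need a more extreme gap. Age may add to the sex bias or offset it; body composition was not quantified.

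The randomised comparison of β-alanine with placebo in MS is not biased. That is not the same as unaffected: with 10 per arm and no stratification, chance sex imbalance can reduce its precision on POST level. A reader might also infer that group-by-time is inflated. That would require training gains to differ by sex or scale with level, and the documents do not establish either.

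**What to change.** - Name the groups in the baseline comparison.
- For every MS-versus-HC comparison of level, replace the unadjusted test with a linear model that includes sex and age.
- Include sex and age in the between-subject part of the repeated-measures model.
- Describe MS-versus-HC differences as observational.

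Sex-by-time and age-by-time terms are needed only if MS-versus-HC differences in training response are to be interpreted. They are optional for the randomised contrast. Matching of controls and stratified allocation are not required.

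**Cost.** About two sentences in the analysis section. Sex already sets the test ramp and age is needed for eligibility, so nothing new is collected. Two degrees of freedom are lost: the two-sided 5% critical t moves from 2.024 (38 df) to 2.028 (36 df), and the critical F with 3 numerator df from 2.866 (36 df) to 2.883 (34 df).

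### The 4x2 ANOVA does not isolate a β-alanine effect, and the plan names no β-alanine versus placebo contrast within MS

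*Combined protocol and SAP*

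**What the plan says.** The statistical plan is two sentences in the protocol's Statistical analysis section. The first reads "Baseline differences between groups and post-intervention differences will be analysed using an unpaired student's t-test" and "a 4x2 ANOVA for repeated measures, respectively". The last word pairs the t-test with baseline and the ANOVA with the post-intervention comparison. The second sentence sets the criterion: "The threshold for statistical significance will be set at p<0.05".

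Under Study design, "MS patients and HC will be randomly allocated to one of four intervention groups". These are MS and healthy controls (HC), each with β-alanine or placebo, 10 per group, measured at PRE and POST. The text writes only 4x2; reading it as four groups by two times is an inference from this design, and the natural one.

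The question is set elsewhere. Under Research objectives, "the primary aim of the present project is to investigate whether carnosine loading improves exercise therapy outcome (exercise capacity, body composition) and performance in MS". The next subsection hypothesises that β-alanine "supplementation in combination with exercise therapy optimizes therapy outcome (exercise capacity, body composition) and performance in this population", the population being MS.

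Nowhere does the document split the four-level factor into disease and supplement, say which ANOVA term is decisive, or name a planned contrast, post-hoc test or multiplicity rule.

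**The concern.** The four groups cross a factor that cannot be randomised (MS or HC) with one that can (β-alanine or placebo). The group-by-time F asks only whether the four mean changes are all equal. It can be significant because MS patients and controls respond differently to training, with the supplement doing nothing.

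Such a difference is plausible on the protocol's own account. The introduction says of training in MS that "effects are lower compared to healthy controls and some other disease populations", although that concerns low-to-moderate intensity programmes and gives no size.

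Two things are at stake. If the F alone is taken as the β-alanine result, it does not answer the aim. If a contrast is picked after a significant F, at least three are open (within MS, within HC, pooled), and the chance of at least one false positive can exceed 5%.

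**Working it through.** The plan contains no power, effect-size or SD figure, so there is none to reproduce.

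**Inputs from the document.** Four groups of 10, two time points, threshold 0.05.

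**Assumptions.** All 10 per group complete. Effects are in SDs of the PRE-to-POST change. Variances are equal unless stated. D is the MS–HC difference in mean change, over a range because no size is given. Tests of a single contrast are two-sided.

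**Step 1: what the named test tests.** With two time points, the group-by-time F equals a one-way ANOVA on change scores, F(3, 36), critical value 2.866. Its noncentrality is λ = 10 × Σ(mean change − grand mean)². With no β-alanine effect and group means 0, 0, D, D, each deviation is D/2, so λ = 10 × 4 × (D/2)² = 10D².

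| D (SD) | λ | P(F significant), no β-alanine effect |
|---|---|---|
| 0.25 | 0.625 | 8.5% |
| 0.5 | 2.5 | 21% |
| 0.8 | 6.4 | 50% |
| 1.0 | 10 | 71% |

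A β-alanine effect of the same size in both populations gives group means D, 0, D, 0 and the same λ. Its rejection rate is therefore identical (71% at 1.0 SD), and the F cannot tell the two situations apart.

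**Step 2: false positives under each reading of a significant F.** Simulation of 400,000 trials, no β-alanine effect, contrasts tested with the pooled 36-df error:

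| D (SD) | F, then within-MS only | F, then any of within-MS, within-HC, pooled |
|---|---|---|
| 0 | 1.9% | 3.7% |
| 0.25 | 2.4% | 4.7% |
| 0.5 | 3.3% | 7.0% |
| 0.8 | 4.4% | 9.7% |
| 1.0 | 4.8% | 10.8% |

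The plan does not say that a significant F is required before any contrast is tested. Without that requirement, choosing among the three contrasts gives about 11% at every D.

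**Step 3: choice of error term for a within-MS contrast.** Type I error if the SD of change differs between MS and HC (ratios assumed):

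| MS SD : HC SD | Error pooled over all 40 (36 df) | MS-only error (18 df) |
|---|---|---|
| 1.25 | 7.5% | 5.1% |
| 1.5 | 9.5% | 5.0% |
| 2 | 12.1% | 5.0% |
| 1/1.25 | 2.8% | 5.0% |
| 1/1.5 | 1.5% | 5.0% |
| 1/2 | 0.3% | 5.0% |

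**Step 4: precision of the MS-only test.** The 95% CI half-width is t(0.975, 18) × √(2/10) = 2.101 × 0.447 = 0.94 SD. Power is 80% at 1.32 SD and 78% at 1.29 SD. With 8 completers per arm the half-width is t(0.975, 14) × √(2/8) = 2.145 × 0.5 = 1.07 SD, and power at 1.29 SD falls to 67%.

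**Step 5: power if β-alanine works equally in both populations, at 0.91 SD.** Within-MS 49% (18 df) or 51% (36 df); omnibus F 62%; contrast pooled over MS and HC 80%.

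**The case against.** The strongest reply is that nobody would report the omnibus F as the β-alanine result. The aim concerns MS, the design pairs an MS β-alanine group with an MS placebo group, and the obvious follow-up is the within-MS contrast. On that reading the false-positive rate is 1.9% to 4.8%, with no inflation. Inflation needs both free choice among contrasts and an MS–HC difference, and with a significant F required first it passes 5% only at the larger assumed D. If the follow-up were Tukey-adjusted (also an assumption), the within-MS rate would be about 1%.

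This is right about size: the rates in Steps 1 and 2 are conditional illustrations, not forecasts. It does not remove the gap. The plan states neither the within-MS follow-up nor an adjustment, so the reassuring rate depends on a rule the document does not contain.

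Three further points stand in part. Unequal variances affect any pooled-error ANOVA, and no SDs are given here; the ratios only show why the error term should be stated with the contrast. Naming a contrast settles which comparison decides, but not multiplicity across the outcomes listed in the aim. A disease-by-supplement-by-time model with a pooled supplement term is also defensible and has more power if the effect is the same in both populations. It would, however, answer a broader question than the one the protocol poses.

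**Conclusion.** The concern holds. Followed as written, the plan produces a 3-df test that does not isolate the randomised comparison in the population named in the aim. The omission is certain from the text. The size of the harm depends on how a significant F would be used and on an MS–HC difference the documents do not quantify. For D from 0.25 to 1.0 SD, with 10 completers per group and equal variances, the erroneous rate is 8.5% to 71% if the F alone is read as the β-alanine result, 4.7% to 10.8% if any of three contrasts may follow it, and below 5% if only the within-MS contrast may follow. This should be fixed, but it is a pre-specification gap and not a flaw in the design, because the four-group data can supply the contrast.

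**What to change.** State in the Statistical analysis section that:

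- the decisive test is the 1-df β-alanine minus placebo difference in PRE-to-POST change within MS, reported with a 95% CI;
- its error term comes from the MS groups only (18 df), or from all four groups (36 df) only with equal MS and HC variances declared as an assumption;
- the supplement-by-time effect pooled over MS and HC, and the supplement-by-disease-by-time interaction, are secondary, each with a 95% CI;
- no β-alanine conclusion rests on the omnibus F;
- the decisive test applies to one named outcome from those in the aim, since the 5% rate covers a single outcome.

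The cost is a few sentences of analysis text, with no extra participants or data. The price is power if β-alanine acts equally in both populations: at 0.91 SD, 49% (18 df) or 51% (36 df) against 62% for the omnibus F, with the pooled secondary contrast at 80%. The change does not cure the limited precision of 10 per arm, so the CI should carry the interpretation.

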All participants will perform a home-based supervised exercise training program. Participants will receive weekly training instructions using a smartphone based heart rate monitor app (Polar $^{\circledR}$). Training involves cycling, performed independently on their personal race bicycle. The exercise training program (6 months) involves 3 week cycles (week I-III). During week I, subjects will perform high volume moderate intensity cardiovascular cycle training (3x/week). Twice a week, subjects perform 3h training sessions (70-80% HR_{max}^{*}) and once a week a 1.5h session will be executed (80-90% HR_{max}). During week II, subjects will perform low volume maximum intensity interval cycle training (3/w). High intensity interval cycle training (HIIT) will consist of 3x maximal sprints (90-100% HR_{max}) of 1.5min, interspersed with 3min rest intervals. A 5min standardized warming up and 5min cooling down will be performed. Week III involves a recovery week where subjects will perform one training session of 1.5h at an exercise intensity of 70-80% HR_{max} and one session of HIIT. Throughout the intervention program at least 3 collective tours will be organized, where all subjects will perform a training session together, to improve group dynamics and motivation.

**obtained from the maximal graded exercise test*

β -alanine supplementation

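### The two-time repeated-measures ANOVA drops anyone without a POST test, and no POST test is provided for participants who stop; if drop-out differs by arm, the β-alanine contrast is biased, in a direction that cannot be known in advance

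*Combined protocol and SAP*

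**What the plan says.** The protocol's Statistical analysis section has two sentences. Baseline differences are tested with an unpaired t-test, and differences after the intervention with "a 4x2 ANOVA for repeated measures"; then "The threshold for statistical significance will be set at p<0.05". SAS is named, but no procedure.

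Under Study design, 20 MS patients and 20 healthy controls are tested at PRE and randomised to 6 months of training "with (MS β , n=10; HC β , n=10) or without" β-alanine, which gives 10 per group. The only follow-up sentence is "Following 6 months of exercise training (POST) measurements will be performed similar to baseline".

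Under Exercise program, the training is home-based cycling in 3-week cycles. In week I, "Twice a week, subjects perform 3h training sessions", with a third session of 1.5 h. Under the ergogenic-potential heading of the Introduction, the protocol says that "early fatigue of contracting musculature during rehabilitation is the predominant cause of exercise cessation", and it expects β-alanine to postpone such fatigue.

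The documents do not define an analysis population, a missing-data method, an expected drop-out rate, or testing of people who stop. Maximal effort on the exercise test is checked by RER, but no rule is given for a test that fails the check, which is another way for a POST value to go missing.

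**The concern.** A comparison restricted to people with both tests is the randomised comparison only if loss to POST is unrelated to outcome or acts in the same way in both arms. Here the programme is demanding and runs for 6 months. By the protocol's own reasoning, the treatment acts on something that makes people stop exercising. Drop-out that differs by arm is therefore plausible, although the protocol does not establish it.

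If it happens, the group-by-time estimate can move away from zero when β-alanine does nothing, and a reader could not tell which way. With 10 per arm, each lost test is also 10% of an arm. A POST test that was not done cannot be recovered later, so this has to be settled before follow-up.

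**Working it through.** **Inputs from the protocol:** 4 groups of 10, PRE and POST, significance at 0.05 (taken as two-sided). **Assumed, because the documents give nothing:** PRE-POST correlation r from 0.5 to 0.8, equal variances, normal outcomes, true effect 0, and 2 or 3 of 10 placebo participants lost. The protocol has no power or drop-out figure to reproduce.

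**1. The ANOVA is a change-score analysis.** On one simulated data set (4 × 10), the group-by-time F of the repeated-measures ANOVA and the F of a one-way ANOVA on POST minus PRE are both 0.74997 (3 and 36 df). No POST means no change score.

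**2. Loss of the least fit (lowest PRE).** The three lowest expected normal order statistics for n=10 are -1.539, -1.001 and -0.656. The expected mean of those who remain is therefore raised by
- 2 lost: (1.539 + 1.001)/8 = 0.3175 SD
- 3 lost: (1.539 + 1.001 + 0.656)/7 = 0.4566 SD

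The mean change among them falls by (1-r) times this, in SD of the outcome. The SD of change is √(2-2r), so in SD of change:

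| r | SD of change | 2 lost | 3 lost |
|---|---|---|---|
| 0.5 | 1.000 | 0.5 × 0.3175 / 1.000 = 0.16 | 0.5 × 0.4566 / 1.000 = 0.23 |
| 0.7 | 0.775 | 0.3 × 0.3175 / 0.775 = 0.12 | 0.3 × 0.4566 / 0.775 = 0.18 |
| 0.8 | 0.632 | 0.2 × 0.3175 / 0.632 = 0.10 | 0.2 × 0.4566 / 0.632 = 0.14 |

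The placebo mean change is too low, so the bias is toward β-alanine. In simulation, conditioning on PRE brings it to about 0.

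**3. Loss of the worst responders (lowest change).** The same order statistics now apply to change itself, whatever r is: 0.32 SD of change (2 lost) or 0.46 (3 lost). On placebo the loss raises the placebo mean, so the bias is against β-alanine. The same loss in the β-alanine arm favours β-alanine.

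**4. Drop-out in both arms** (about 4,000 simulated trials per scenario, r = 0.5 and 0.8, bias in SD of change, negative = against β-alanine).

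| Drop-out | Bias, completers | Type I error |
|---|---|---|
| 20% / 20%, random | about 0 | 0.046-0.053 |
| 20% / 20%, equally selective on response | about 0 | 0.047-0.052 |
| Placebo 30%, β-alanine 10%, both selective on response | -0.21 | 0.074-0.079 |
| β-alanine 30%, placebo 10%, both selective on response | +0.21 to +0.22 | 0.07 |
| Placebo 30%, β-alanine 10%, both selective on PRE | +0.06 to +0.10 | 0.047-0.050 |

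A likelihood model that keeps PRE-only participants removes the bias in the last row. It leaves 0.16-0.19 in the two rows above it, and up to 0.31 in a harsher scenario (placebo 30% selective on response, β-alanine 10% random). With everyone tested at POST, bias is within 0.014 and type I error is 0.044-0.056 throughout.

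**5. Precision.** Going from 10 to 8 per arm widens the standard error by √(10/8) = 1.12. The difference detectable with 80% power moves from 1.32 to 1.51 SD of change. In the other direction, conditioning on PRE gives a large-sample variance of (1-r²)/(2-2r) = (1+r)/2 of the change-score variance: 0.75 at r = 0.5 and 0.90 at r = 0.8.

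**The case against.** The strongest reply is that this is silence in a very short section, not a stated exclusion. No SAS procedure is named, and a mixed-model fit would keep PRE-only records. The POST sentence can be read as a time point for all 40. The fatigue sentence may mean fatigue that ends a bout of exercise, not withdrawal from a trial. The programme is supervised, with weekly instructions, recovery weeks and group rides, and the placebo is identical in taste and appearance. All of this stands. A reader might infer that the protocol prescribes a completers-only analysis or leaves stoppers untested; it says neither. What remains is that the method as named, in its classical form, needs both values, and nothing else in the text secures them.

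A reader might also infer that drop-out would flatter β-alanine, with the loss of unfit participants and of poor responders adding up. The arithmetic does not support this: on placebo the two act in opposite directions, and the loss of poor responders is the larger effect.

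Finally, the bias that a better model alone removes is modest. At r = 0.7, losing the 2 or 3 least fit from placebo only is 0.26 or 0.36 of the contrast's standard error, with type I error 0.058 or 0.064. This also stands, and is why POST testing comes first in the fix.

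**Conclusion.** The point holds as a conditional one. A classical ANOVA on PRE and POST drops participants without POST, and the protocol provides no POST test for those who stop. Bias in the β-alanine contrast then requires drop-out that differs between arms in rate or in its relation to fitness or response. The protocol's fatigue rationale makes this plausible but does not show it.

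Under the stated assumptions, losing 2 or 3 of 10 placebo participants shifts the contrast by between 0.10 and 0.23 SD of change toward β-alanine if the least fit go, and by about 0.32 to 0.46 against it if the worst responders go. Conditioning on PRE removes the first; no model fully repairs the second. The direction cannot be predicted, so a completers' result could not be defended as conservative. The sizes are illustrations and would change with the real drop-out pattern and correlation.

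**What to change.** 1. **Study design (the main part).** State that POST testing is offered at 6 months after the start to every randomised participant, whether or not tablets or training were stopped.
2. **Statistical analysis.** Replace the ANOVA with a linear mixed model with PRE and POST as outcomes, baseline means constrained equal between β-alanine and placebo within each population, and every randomised participant included in the assigned arm. Say in the same paragraph how an exercise test that fails the RER check is handled.

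The second step without the first relies on data missing at random and is only a partial remedy. Even with complete data it gains precision from the PRE value that is already collected.

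The cost is a sentence in Study design, a paragraph of analysis text, and some effort to bring back people who stopped. The as-assigned estimate may be smaller than the completers' estimate.
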